Specific Aim 2: Brain Changes - We aim to determine if white matter fiber tracts show improved integrity as measured by diffusion imaging (DKI) before, after a 2-week treatment taVNS-paired feeding course, and whether treatment improves neuronal energetics in the basal ganglia as measured by magnetic resonance spectroscopy (MRS). Unsedated MRS and DKI imaging will last approximately 40 minutes, and will be done before and after the two-week taVNS-paired rehab treatment session. The changes in white matter tract diffusion parameters and N-acetylaspartate (NAA) and glutathione (GSH) concentration in the basal ganglia and thalamus will be compared with published changes of these parameters over gestational age in preterm infants (14, 15) and with our own MRS data in preterm and HIE infants who did not receive taVNS.

We will perform DKI to determine the effects of taVNS on plasticity, and to identify areas of the brain involved in afferent vagal activation. We propose utilizing the concurrent taVNS/fMRI method developed by [name] at MUSC to determine whether taVNS activates the CNS and afferent vagal network in a subset of preterm and term infants in the study.

B. BACKGROUND AND SIGNIFICANCE

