from 2-10 and for 0.5 – 5 mA. Moreover, the safe use of TENS for the iontophoresis necessary for the sweat test in neonates to confirm cystic fibrosis, supports its minimal risk designation in neonates (43). The investigators in these neonatal and infant studies as well as research conducted by Drs. [name] and [name] in adults at this institution, used the same frequency and intensity (10Hz, 0.5-5mA), and no painful or ill effects have been observed. Not only is TENS safe in all populations and is FDA cleared, in the case of VNS, we already have substantial evidence of dose response in adults ([name], [name]) as well as efficacy and safety. The dosing parameters chosen in this study were found to be safe and have positive brain imaging results.

The purpose of this study is primarily to determine feasibility of the proposed taVNS dose and duration with a paired feeding, that has minimal negative effects and confers positive functional and CNS structural benefits. As this is a pilot study, we do not know the exact intensity of the stimulus that our infants will perceive. We have built in a dose determination during rest and during feeding for perceptual threshold. We also have an immediate reduction built in for safety if it causes discomfort, and we have planned for a gradual increase in the duration of treatment over the first feeding sessions to determine the tolerability. We have included the protocol for the perceptual threshold determination for clarification.

We hope to verify that the protocol for delivering taVNS-paired feeding will effectively align with regular, pre-existing OT rehabilitation performed in nearly all pre-term neonates, and that taVNS-paired feeding improves their ability to feed. We anticipate that taVNS-paired feeding treatments can be conducted in a feasible, time and cost effective manner. Our secondary purpose is to understand with brain imaging how taVNS may improve the CNS circuitry and metabolism, which correlates with the specific early motor task of learning to feed. As long term developmental data is always important in studies of infants, we will also look at preliminary data to see if this effect can be linked to long-term functional ability.

Diffusion MRI (dMRI) may determine effects of taVNS on plasticity.

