Rapid changes in diffusion have been noted with electrical stimulation accompanied by a 20-45% increase in extracellular water in animals and human volunteers(3-5). On a cellular level, the diffusion changes are believed to indicate increased Na⁺/K⁺ATPase activity(6), and ionic and water movement through neuronal and glial membranes(5). These diffusion changes in white matter (WM) tracts have been proposed as an alternative to BOLD fMRI(3), and may be particularly applicable to measuring direct changes after taVNS in this neonatal and infant population after global HI brain injury. In addition, we will use DKI which is more sensitive in neonates and infants, who generally have lower FA and higher kurtosis values. This is a novel application of DKI as an indication of vagal-mediated central effects induced by taVNS paired feeding.

This research proposal will further develop a noninvasive vagus nerve stimulation as an assistive tool in the rehabilitation of neonates born with feeding deficits. We will confirm the safety of this new technique using fluoroscopic imaging as well as its effect on brain plasticity using advanced structural and functional neuroimaging.

We hypothesize, based on the paired VNS studies in animals and humans to date as well as human noninvasive VNS studies conducted here at MUSC, that taVNS-paired feeding in pre-term neonates will be feasible, safe and not worsen swallowing problems and perhaps improve them. Additionally, we hypothesize that ta-VNS-paired feeding will accelerate pre-term neonates' ability to learn feeding

sensorimotor skills, which will be apparent in increased volume of milk consumed and longer oral feeding durations. If feeding behavior is improved, then we further expect decreased levels of functional impairment as compared to baseline STEP tests after receiving taVNS-paired feeding. These hypotheses regarding neonatal health and improvement, while vital in understanding the impact of taVNS-paired rehab in pre-term neonates, come second to the primary hypothesis that this novel treatment is safe and feasible.

C. PRELIMINARY STUDIES

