[name], Ph.D, obtained his doctorate under [name], and has extensive experience and background in clinical TMS and taVNS, especially in the development of novel protocols for neurological disorders. His thesis work involves systematic elucidation of the dose response of taVNS on heart rate, use of heart rate as a biomarker of taVNS effect, and the use of taVNS with fMRI in determining pathways and regions affected by taVNS in adults. He determined that the 'on' pulse heart rate change was a mean of -3 beats per minute (bpm) while the 'off' pulse heart rate change was +6 bpm. Although these are statistically significant and measurable changes, they are physiologically insignificant. Nevertheless, this will be an important biomarker for infants, but is not expected to result in safety concerns. [name] careful and thorough studies lay the safety and efficacy groundwork for the current proposal.

D. RESEARCH DESIGN AND METHODS (including data analysis)

Due to the novelty of these studies, [name] will be present for each taVNS-paired feeding session conducted in the first participants, and as needed thereafter. [name] and or [name] will monitor taVNS effects. If any adverse events are noticed which are not described in the consent or are serious, we will inform the IRB before continuing with the next enrolled subject. Importantly, all of these methods have been done before, and published by our and other groups in adults, and we believe these extra precautions will assure the safety and well-being of any participants enrolled.

taVNS-paired feeding to enhance feeding behavior in neonates

Screening

Prospective participants will be identified by the PI ([name]) at the MUSC neonatal intensive care units (Level II and III), and checked for potential inclusion (please see the uploaded taVNS screening form). [name], and other clinical OTs based in the nursery may also mention the study to parents and refer them to [name] if they are interested in participating.

Participants

Inclusion criteria:

Infants must be clinically stable, on minimal respiratory support (nasal cannula, or room air), in discussions about Gtube placement for poor po feeding and are currently greater than or equal to 39 weeks post-menstrual age and

- 1) If born premature have been working on oral feeding for 30days;
or

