For safety we will compare HR changes from baseline to during taVNS within subjects. We will compare treatment before and after the taVNS-paired feeding treatment for the rate of feeding volume increase, and days to full po feeds. We will use repeated measures ANOVA to analyze repeated measures such as HR over 5 minutes and mean daily feeding volumes in 7-10 day epochs. We will analyze the number of infants who reach full feeds vs requiring G-tube during taVNS-paired feeding, between once and twice daily stimulation by Chi-squared. We will assess differences in kurtosis parameters from pre-to post taVNS scans by paired t-test, and between those that reach full oral feeds vs those that require a Gtube by unpaired t-test.

Estimated Difficulties, Limitations and Time Frames

Estimated Difficulties. Many of the initial parameters for taVNS in humans, such as frequency and pulse width, were accomplished in trials at MUSC by [name] et al. that were approved by the IRB. In one sense, we will be shrinking many of the components into miniature form to deliver stimulation to neonates and infants. In spite of the clear differences in size and skin between the neonatal and adult ear, the custom electrodes have been fitted to several different weights of infants (2.5-4.0 kg).

Limitations. We will not be delivering a SHAM stimulation paradigm (electrodes and Digitizer with appearance of taVNs treatment without actual current). Our goal is to determine safety and feasibility of active treatment with a dose response in order to investigate whether this should be administered in a larger randomized control trial. In this respect, the comparison we lose in not having a SHAM stimulation is offset by the validation we will receive in the safety and feasibility of active treatment. We will compare our overall results with characteristics of infants who required a Gtube from [name] and [name]'s publications.

Estimated Time Frames. The duration of the study will likely be ~4 years, with 2 years of active enrollment and 18 months of follow-up.

E. PROTECTION OF HUMAN SUBJECTS

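### The paired pre/post kurtosis test cannot separate a taVNS effect from two to three weeks of brain maturation, and the comparison promised in Aim 2 names no identifiable diffusion source and is missing from Data Analysis

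*Combined protocol and SAP*

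**What the plan says.** Data Analysis (section D) gives two tests for the diffusion data. The first is "We will assess differences in kurtosis parameters from pre-to post taVNS scans by paired t-test". The second continues the sentence: "and between those that reach full oral feeds vs those that require a Gtube by unpaired t-test". It does not say whether the second test uses post-treatment values or changes.

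Study Design gives active stimulation to every consented infant, and Limitations states: "We will not be delivering a SHAM stimulation paradigm". Specific Aim 2 places the scans before and after a two-week course, while Study Design describes a course of 2 to 3 weeks.

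The purpose of the imaging is stated in Specific Aim 2: "We will perform DKI to determine the effects of taVNS on plasticity". Background and Significance ranks it: "Our secondary purpose is to understand with brain imaging how taVNS may improve the CNS circuitry and metabolism".

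Specific Aim 2 also anticipates maturation. It says that changes in tract diffusion parameters, NAA and GSH "will be compared with published changes of these parameters over gestational age in preterm infants (14, 15") and with the site's own spectroscopy (MRS) data in untreated infants.

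**The concern.** A paired t-test asks whether mean change differs from zero. That is the right question only if an untreated infant would show no change between scans. Aim 2 assumes otherwise, since it proposes to set these parameters against their published course over gestational age. With no untreated infants in the test, a significant result would be expected from growth, from taVNS, or from both.

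The feeding-outcome test does not fill the gap. Both of its groups are treated, so it can show an association between imaging and feeding but not an effect of stimulation.

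What is at stake is the secondary imaging aim. The trial is meant to inform whether a larger randomized trial should follow, and a significant paired test could be offered as evidence of mechanism when growth alone would produce it.

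**Working it through.** **Is there an untreated diffusion benchmark in the plan?**

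- *Published change.* Aim 2 cites references 14 and 15. By title in the reference list, both are proton spectroscopy papers, one on metabolite composition in early brain development and one on neonatal brain injury. Neither title mentions diffusion.
- *Site data.* The untreated infants' data are described as MRS.
- *Historical controls.* Study Design and Limitations describe infants who received G-tubes, with no mention of imaging.
- *Data Analysis.* It contains no comparison with any of these.

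Two limits apply. The contents of references 14 and 15 could not be read, and part of the document, apparently in Preliminary Studies, was not available. A numbering fault is also possible: the diffusion paragraph in Background cites references 3 to 6, and none of those is a diffusion paper by title.

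**What does the paired test do if taVNS has no effect?**

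The plan gives no effect size, SD, alpha, drift or number of scan pairs for this analysis, so there is no figure to reproduce. The following is an illustration.

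Inputs:
- n = 40 is the maximum enrolment (Study Design); n = 10 and 20 are assumed smaller numbers of complete pairs.
- Two-sided alpha of 0.05 is assumed.
- Drift d is the mean maturational change divided by the SD of within-infant change, assumed to be 0.2, 0.5 or 0.8. The documents give none, in particular not for infants who are "currently greater than or equal to 39 weeks post-menstrual age".

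Model: change = m + τ + error, where m is maturation, τ is the taVNS effect and the error has SD σ. The test sees only m + τ. With τ = 0 and d = m/σ, the statistic follows a noncentral t with n − 1 degrees of freedom and noncentrality d√n. The rejection probability is P(|T| > t(0.975, n − 1)).

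Worked case, n = 20 and d = 0.5: noncentrality 0.5 × √20 = 2.236; critical value 2.093; rejection 0.5645, or 56%.

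| Scan pairs | Critical t | d = 0.2 | d = 0.5 | d = 0.8 |
|---|---|---|---|---|
| 10 | 2.262 | 9% | 29% | 62% |
| 20 | 2.093 | 14% | 56% | 92% |
| 40 | 2.023 | 23% | 87% | over 99% |

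With no drift the rate is 5%. Any non-zero drift raises it, and more scan pairs make it worse. Simulation at n = 40 (20,000 runs) gave 0.87 at d = 0.5, in agreement.

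**Does an untreated comparison cure it?**

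A two-sample t-test on change, with 40 treated and 40 untreated infants sharing the same drift, rejected in 0.048 to 0.051 of 20,000 simulated studies for drifts from 0 to 0.8 SD. Shared drift cancels.

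**What does that cost in precision?**

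The 95% CI half-width, in SD of change, is t(0.975, n − 1)/√n for the paired mean. Against an untreated reference of equal size and SD it is t(0.975, 2n − 2) × √(2/n).

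| n (per group) | Paired mean | Treated minus untreated |
|---|---|---|
| 10 | 2.262/3.162 = 0.72 | 2.101 × 0.447 = 0.94 |
| 20 | 2.093/4.472 = 0.47 | 2.024 × 0.316 = 0.64 |
| 40 | 2.023/6.325 = 0.32 | 1.991 × 0.224 = 0.45 |

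**The case against.** The best reply is that the investigators saw the problem. Aim 2 commits to a maturation comparison and lists diffusion parameters in it. A reader might therefore infer from this point that the plan ignores maturation; the documents do not support that. What remains is narrower: no diffusion source can be identified, and the comparison does not reach the analysis section. If the citations were simply misnumbered, or if untreated imaging is described in text not available here, the first half is repaired by a correction. The second half still stands.

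Background also contains the sentence "This is a novel application of DKI as an indication of vagal-mediated central effects induced by taVNS paired feeding". It is tempting to read this as a causal claim about the before/after contrast. It follows a discussion of rapid diffusion changes under electrical stimulation, so it does not clearly refer to scans weeks apart, and the point does not rest on it. The statement of purpose in Aim 2 is sufficient.

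Data Analysis speaks only of assessing differences and sets no causal decision rule. The lack of sham is disclosed, the trial is labelled open-label safety and feasibility, and imaging is secondary. All of this is fair and lowers the weight. It does not settle attribution, because the protocol offsets the missing sham by what it will learn about safety and feasibility, which says nothing about why an imaging measure changed.

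Finally, the rejection rates rest on assumed drifts and run from 9% to over 99%. They show how the test behaves, not how large the problem will be here. At 0.2 SD with 10 or 20 pairs the rate is 14% or less.

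**Conclusion.** The point holds for the secondary imaging aim. As planned, the paired kurtosis test cannot distinguish a taVNS effect from maturation, and the promised external comparison is neither tied to an identifiable diffusion source nor carried into the analysis. That conclusion needs only the design and Aim 2's own expectation of change with age. The size is unknown: at an assumed drift of 0.5 SD the false attribution rate would be 29%, 56% or 87% with 10, 20 or 40 pairs, under two-sided 5% testing and normally distributed changes.

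Two stronger readings are not supported. A reader might infer that a significant paired result would be wrong; it would be uninterpretable as to cause, which is different. A reader might also infer that the full-feed versus G-tube test is biased. Nothing here shows that; it is under-specified, and it cannot speak to a taVNS effect because both groups are treated. Safety and feasibility conclusions are untouched.

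**What to change.** In Data Analysis:

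1. Report the mean paired kurtosis change with its 95% CI as descriptive, and state that it includes maturation. Do not use it as evidence of a taVNS effect unless change is compared with a named untreated diffusion reference or data set at similar postmenstrual age and scan interval. If the citations in Aim 2 were misnumbered, correct them and write that comparison into Data Analysis.
2. State that the full-feed versus G-tube comparison is of change (post minus pre), and that it is exploratory and associational.

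The cost is wording and a weaker claim under Aim 2; no extra infants or study scans are needed for the descriptive version. If the sponsor keeps the causal claim and finds an untreated reference of equal size and SD, the interval widens by the amounts tabulated above, for example from ±0.47 to ±0.64 SD with 20 per group.

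### The diffusion analysis tests several kurtosis parameters in several unnamed tracts with no deciding contrast and no error control, yet the protocol says it will confirm an effect on brain plasticity

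*Combined protocol and SAP*

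**What the plan says.** Section A, Specific Aim 2, sets the imaging question: "We aim to determine if white matter fiber tracts show improved integrity as measured by diffusion imaging (DKI"). The tracts are plural and none is named. Scans are taken before and after the two-week course.

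Section D, Data Analysis, gives the only statistical methods for imaging. There are two:

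- Pre versus post: "We will assess differences in kurtosis parameters from pre-to post taVNS scans by paired t-test".
- By feeding outcome: "between those that reach full oral feeds vs those that require a Gtube by unpaired t-test".

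The kurtosis parameters are also plural and unnamed. No significance level, primary imaging contrast or adjustment is stated, and the imaging tests are not called exploratory.

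For spectroscopy, Specific Aim 2 says: "N-acetylaspartate (NAA) and glutathione (GSH) concentration in the basal ganglia and thalamus will be compared with published changes", and also with the site's own untreated infants. No test is named for this, and Data Analysis does not mention spectroscopy.

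Near the end of section B, the protocol says it will confirm the safety of the technique and also "its effect on brain plasticity using advanced structural and functional neuroimaging". Section B also calls brain imaging a secondary purpose and puts safety and feasibility first.

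**The concern.** Each t-test would be read at its own nominal level, and the plan leaves open how many there are. A set of parameters crossed with a set of tracts gives many chances for one p-value below 0.05 when nothing has changed. With no measure singled out beforehand, the one that happens to be significant can be reported as the structural finding.

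Imaging is one of only two Specific Aims. Section B describes the study's purpose as including structural benefit to the central nervous system, and calls this use of diffusion kurtosis imaging novel, so the protocol points to no customary tract or parameter as a default. A chance finding would support the mechanism claim and could be cited when a larger randomised trial is considered.

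**Working it through.** **Inputs**

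- Tests planned: a paired and an unpaired t-test on kurtosis parameters (section D, Data Analysis).
- Number of parameters and tracts: not stated; both are plural (section D; Specific Aim 2). The smallest plural reading is 2 × 2 = 4 measures. This is an assumption.
- Alpha: not stated. Two-sided 0.05 per test is assumed.
- Correlation between measures: not stated. The range 0 to 0.8 is used.
- Infants: up to 40 (section D, Study Design). The number with paired scans is not given.

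The plan states no error rate, so there is no figure to reproduce.

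**Step 1. Pre-post comparison only, independent measures.** The chance of at least one p < 0.05 with no true change is 1 − (1 − 0.05)^m.

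- m = 1: 0.05
- m = 4: 1 − 0.95^4 = 1 − 0.8145 = 0.1855

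**Step 2. Correlated measures.** Diffusion measures from one brain are likely to be correlated. Simulating 4 equally correlated normal test statistics (400,000 draws) gives:

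| Correlation | Chance of at least one p < 0.05 |
|---|---|
| 0 | 0.19 |
| 0.5 | 0.16 |
| 0.8 | 0.11 |

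So the smallest plural reading gives roughly two to four times the nominal 0.05.

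**Step 3. Where the chance passes one half.** For independent tests:

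- m = 13: 1 − 0.95^13 = 0.487
- m = 14: 1 − 0.95^14 = 0.512

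About 14 independent tests are needed, and more if they are correlated. The documents do not say whether so many will be run.

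**Step 4. Favourable direction only.** If only a change towards better integrity counts, each test contributes 0.025:

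- m = 4: 1 − 0.975^4 = 0.096
- m = 27: 0.495; m = 28: 0.508

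**Step 5. What is left out of the count.** Spectroscopy is excluded because no test is planned for it. The unpaired comparison is excluded from the main figure because it compares treated infants with each other. Adding it on the same 4 measures would make 8 tests and 1 − 0.95^8 = 0.34 if independent, but those 8 tests answer two different questions.

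**Step 6. A separate problem: maturation.** Suppose development alone shifts a measure by a given fraction of the standard deviation of the change score. The sizes are assumptions. The chance that a single paired t-test is significant, from the noncentral t distribution, is:

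| Shift (SD of change) | n = 20 | n = 40 |
|---|---|---|
| 0.2 | 0.14 | 0.23 |
| 0.5 | 0.56 | 0.87 |

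This is not a chance finding, and adjusting for the number of tests does not remove it.

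**The case against.** The strongest reply is that imaging is secondary in an open-label pilot of up to 40 infants. No success rule rests on it, and the Limitations text in section D ties the larger trial to safety, feasibility and dose response. Specific Aim 2 is also worded as a question, not as a promised result. All of this stands, and it limits the weight of the point. It does not answer the wording in section B, which promises confirmation, and section D does not label the tests exploratory.

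A reader might infer that a positive brain effect is likely by chance alone. The documents do not support that. It would need about 14 independent tests, or about 28 if only favourable results count, and the plan gives no count.

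A reader might also add the metabolites: two metabolites, two regions and two references would make eight more tests. The plan names no test for them, so that count would be invented. The gap there is a missing analysis. The search "to identify areas of the brain involved in afferent vagal activation" likewise has no stated test.

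The two t-test families should not be pooled into one false-effect rate for the stimulation. Every infant receives active treatment, so a false positive between the feeding-outcome groups is not in itself a false taVNS effect.

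Finally, it can be said that maturation is the larger threat to the pre-post comparison. That may be so, since Step 6 shows it can dominate. It is a further limitation and does not excuse the missing error control.

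**Conclusion.** The concern holds in a limited form. The plan states a method, separate t-tests over several unnamed diffusion measures, that carries no control of false positives, and it attaches a confirmatory claim to the result. On the smallest plural reading the family-wise error for the pre-post question is about 0.19 with independent measures and 0.11 at correlation 0.8, against a nominal 0.05. These figures rest on an assumed two-sided 0.05 and an assumed 2 × 2 set; larger sets give larger errors. The change should be made, but because imaging is secondary and no decision rule depends on it, the point does not threaten the trial's primary safety and feasibility conclusions.

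**What to change.** Make these changes before any scan is analysed:

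1. In section D, Data Analysis, name one diffusion measure in one tract, or one average over a fixed set of tracts, as the single deciding imaging contrast for the pre-post comparison. State its significance level. One contrast at 0.05 keeps the error for the imaging claim at 0.05.
2. List the remaining kurtosis parameters and tracts, and apply the Benjamini-Hochberg procedure at a 5% false discovery rate across them.
3. Label those measures, the comparison of full-feeds with G-tube infants, and all spectroscopy results as exploratory.
4. In section B, replace *confirm* with *explore* for the effect on brain plasticity.
5. State that a pre-post change cannot by itself be attributed to taVNS, because two weeks of maturation can also produce it and multiplicity control does not deal with that.

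The cost is protocol wording and a few lines of analysis code; no extra scans are needed. The downside is that some nominally significant tracts will no longer count as findings.
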